Methodology

Study design and Patient selection

Patients with a history of migraine diagnosis who presented at the Research Polyclinic of Karabuk University Training and Research Hospital for wet-cupping therapy in the period May 2016-January 2018 were included in the study. Patients were excluded if they had a history of head and neck surgery, a diagnosis of sinusitis, a diagnosis of fibromyalgia and inflammatory disease (rheumatism, infection etc.), were pregnant, had a diagnosis of cancer, bleeding disorder and widespread skin disease, malignant hypertension or any other disease which could cause headache. The diagnosis of migraine was confirmed by an experienced neurologist and the migraine type was determined. The medical treatments of the patients were reviewed and MIDAS was applied to determine the baseline score. In addition to the medical treatment, WCT was applied once a month, 3 times (Day 0, 30, 60). At the end of the 3rd month patients were allocated into two parallel arms. They were randomly assigned to the intervention group or control group in a double blind manner by the sealed opaque envelope technique. Intervention group continued WCT whereas patients in the control group discontinued the treatment. MIDAS was applied again at the end of the 6th and 12th months to both of the groups. Disability values in the 6th and 12th months were evaluated with MIDAS between those who continued treatment (Group 1) and those who did not (Group 2). Approval for the study was granted by Turgut Ozal University Ethics Committee, with number 99950669/236, dated 30.06.2014. Study design, application procedures and any possible side effects were explained to the study participants and informed consents obtained. All procedures performed in studies involving human participants were in accordance with the ethical standards of the institutional and/or national research committee and with the 1964 Helsinki declaration and its later amendments or comparable ethical standards.

MIDAS

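### Does the protocol commit to comparing MIDAS between the arms without using baseline MIDAS or migraine type?

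*Protocol*

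**What the plan says.** Everything relevant stands in the protocol's Methodology, under Study design and Patient selection.

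- At entry, "MIDAS was applied to determine the baseline score". For type, "The diagnosis of migraine was confirmed by an experienced neurologist and the migraine type was determined".
- All patients then have three monthly wet-cupping sessions, on Days 0, 30 and 60, on top of their medical treatment.
- Randomisation follows: "At the end of the 3rd month patients were allocated into two parallel arms". No MIDAS at month 3 is described.
- For follow-up, "MIDAS was applied again at the end of the 6th and 12th months to both of the groups".
- The between-arm comparison is given in one sentence: "Disability values in the 6th and 12th months were evaluated with MIDAS between those who continued treatment" and those who did not.

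The protocol has no section on statistical methods. It states no sample size, significance level, power, effect size or standard deviation.

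**The concern.** Two useful covariates are measured before allocation, and the one sentence describing the comparison gives neither a role. It speaks of disability values at months 6 and 12. It does not mention change from baseline or adjusted values. Read literally, it could describe a plain comparison of follow-up scores.

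If so, the choice would matter. No minimum MIDAS score is required for entry, and the MIDAS section defines grades from 0-5 points up to 21 or more, so patients of very different severity could be enrolled. No stratification of the randomisation is described. Severity at entry could then add noise to the comparison, and a chance imbalance would be left uncorrected. Adjusting for a score taken before randomisation is valid, usually improves precision, and needs no data beyond what is already collected.

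**Working it through.** **Step 1: what the sentence fixes.** The elements of an analysis, set against the wording:

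| Element | Stated in the protocol? |
|---|---|
| Instrument | Yes, MIDAS |
| Time points | Yes, months 6 and 12 |
| Groups | Yes, cupping continued or discontinued |
| Test or model | No |
| Follow-up value or change as the analysed quantity | Not settled |
| Covariates | No |
| Transformation | No |

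Nowhere does the protocol call the values raw or unadjusted, or say that baseline is left out. A t-test, a rank test, an analysis of covariance and a mixed model would all evaluate month-6 and month-12 disability between these groups.

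**Step 2: what is at stake if the analysis were unadjusted.** There is no figure in the protocol to reproduce, so this step is illustrative. All inputs are assumptions: two-sided alpha 0.05, 80% power, standardised difference 0.5, equal allocation, and a correlation r between baseline and follow-up MIDAS.

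- Unadjusted size per arm: 2 × (1.960 + 0.842)² / 0.5² = 62.8, rounded up to 63, with power 80.1%.
- Variance factor with adjustment for one baseline covariate: 1 − r².
- Equivalent patients lost by not adjusting: 1/(1 − r²) − 1.
- Variance factor for a change score, with equal variances at both times: 2(1 − r).

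| r | 1 − r² | Equivalent patients lost | Adjusted power at 63 per arm | Change-score factor |
|---|---|---|---|---|
| 0.1 | 0.99 | 1.0% | 80.5% | 1.8 |
| 0.3 | 0.91 | 9.9% | 83.7% | 1.4 |
| 0.4 | 0.84 | 19.0% | 86.5% | 1.2 |
| 0.5 | 0.75 | 33.3% | 90.0% | 1.0 |
| 0.6 | 0.64 | 56.2% | 93.9% | 0.8 |
| 0.7 | 0.51 | 96.1% | 97.6% | 0.6 |

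In a very small trial, the degree of freedom spent on the covariate matters too. With the approximate factor (1 − r²)(1 + 1/(N − 4)), a total N of 20 and r = 0.2 give 0.96 × 1.0625 = 1.02, a slight loss.

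**Step 3: where this trial lies in that range.** The protocol gives neither r nor N, so it cannot be placed. The timing also gives no assurance of a high r. MIDAS looks back three months, so the baseline score describes the three months before Day 0. The month-6 score describes months 3 to 6, and the month-12 score months 9 to 12. The gaps between the baseline window and these windows are 3 and 9 months, and the first three months contain three cupping sessions for everyone. The correlation may therefore be weaker than that of a score taken at randomisation.

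**Step 4: bias.** An unadjusted difference between randomised arms is unbiased over the randomisation, and its standard error already allows for chance imbalance in severity. Whether to adjust is a question of efficiency.

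**The case for a change.** The strongest reply is that the sentence is the protocol's whole account of the comparison, is in the past tense like a report of what was done, and names follow-up values only. On that reading it fixes the comparison, and the baseline score is collected without any use in it. The arithmetic also supports the principle: at correlations of 0.4 to 0.6, adjustment removes 16% to 36% of the outcome variance, and 80% power becomes roughly 86% to 94%.

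Part of this stands. Both covariates are collected, the protocol mentions no adjustment, and adjusting for a prognostic baseline is generally good practice.

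The rest does not follow. A sentence that names outcome, times and groups does not exclude covariates, and recording a baseline score gives no reason to think it will be ignored. The range 0.4 to 0.6 is assumed, and weaker values are equally compatible with the design. No baseline distribution of MIDAS is given, so a wide spread of severity is possible but not shown. Nothing is said about the prognostic value of migraine type.

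The adjusted analysis is also not always free. Modelling log(MIDAS + 1) would move the effect from a difference in lost days towards a ratio. A month-3 covariate would need a measurement that the protocol does not describe.

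**Conclusion.** This is not an error in the protocol. The protocol states no unadjusted analysis; it leaves the method open on a matter that a SAP commonly settles, and the SAP is not shown. The possible loss of precision runs from about 1% to 96% in equivalent patients for assumed correlations of 0.1 to 0.7. Nothing in the protocol narrows that range, and no bias would arise at any point in it. The conclusion rests on reading the comparison sentence as naming outcome, time points and groups. It would change if the SAP, or a model stated elsewhere, showed that the arms are compared without baseline MIDAS.

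### Does naming the compared groups by whether patients continued wet cupping make this an as-treated comparison that breaks the randomisation?

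*Protocol*

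**What the plan says.** The text is in the protocol's Methodology, under Study design and Patient selection. Everyone receives three monthly WCT sessions (days 0, 30 and 60) alongside medical treatment. After that:

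- **Timing of allocation:** "At the end of the 3rd month patients were allocated into two parallel arms".
- **Method:** "They were randomly assigned to the intervention group or control group in a double blind manner by the sealed opaque envelope technique".
- **What each arm does:** "Intervention group continued WCT whereas patients in the control group discontinued the treatment".
- **Assessment:** "MIDAS was applied again at the end of the 6th and 12th months to both of the groups".
- **Comparison:** MIDAS disability at months 6 and 12 is evaluated "between those who continued treatment (Group 1) and those who did not (Group 2".

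The labels Group 1 and Group 2 appear only in that last sentence. The protocol does not equate them in so many words with the intervention and control groups. It names no analysis population and does not say how a patient who departs from the assigned course is to be classified.

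**The concern.** The arms are named by assignment, whereas the compared groups are named by what patients did. The two agree only while everyone adheres. Applied word for word, the comparison sentence would put an intervention patient who gave up cupping into Group 2, and a control patient who went on being cupped into Group 1.

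Such departures are conceivable in this setting. The participants are "Patients with a history of migraine diagnosis who presented at the Research Polyclinic of Karabuk University Training and Research Hospital for wet-cupping therapy", so controls are asked to give up something they came for. Each session involves skin incisions and bloodletting, which is a burden on those asked to continue. The last assessment comes nine months after allocation (month 12 minus month 3).

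Stopping or seeking treatment may well depend on how the migraine is going. If patients doing badly left Group 1 and were counted in Group 2, continued cupping could appear to help when it does nothing. Only the comparison of patients as assigned is protected by randomisation.

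**Working it through.** **Step 1: read the comparison sentence in its place.** The protocol gives no sample size, alpha, power, SD or dropout rate, so there is no figure of its own to reproduce. The question is what the labels refer to. In order, the text:

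1. forms two arms at random;
2. says that one arm continued WCT and the other discontinued it;
3. says that MIDAS was given to both groups, and the only groups mentioned so far are the two allocated arms;
4. compares those who continued with those who did not.

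Continuing and stopping are the randomised strategies themselves. Item 4 repeats the terms of item 2 and adds numbers. Nothing between them introduces a second classification, and no sentence moves a patient from one group to the other.

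**Step 2: what would follow if the literal reading were applied.** Every input here is assumed; none is in the protocol. Let there be no true effect, equal arms and a standardised score on which higher is worse. A fraction f of the intervention arm stops and a fraction g of controls takes up cupping. In each case these are the patients highest on a latent variable that correlates ρ with the score. Write φ(f) for the standard normal density at the upper f point: φ(0.10) = 0.1755 and φ(0.20) = 0.2800, with φ(0) = 0.

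First, with stopping in the intervention arm only (g = 0):

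bias (Group 1 minus Group 2) = -ρφ(f)/(1 - f) - ρφ(f)/(1 + f)

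- f = 0.10, ρ = 0.5: -0.08775/0.9 - 0.08775/1.1 = -0.0975 - 0.0798 = **-0.177 SD**
- f = 0.20, ρ = 0.5: -0.1400/0.8 - 0.1400/1.2 = -0.1750 - 0.1167 = **-0.292 SD**
- ρ = 0.3 scales these by 0.6: -0.11 and -0.17 SD

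Simulation with 50 per arm and ρ = 0.5 gives false-positive rates, against a nominal 5%, of about 13 to 14% at f = 0.10 and about 29% at f = 0.20. Analysis as assigned stays near 5%.

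**Step 3: allow departures in both directions.** The worry itself rests on both kinds of departure. The general form is

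bias = ρ[φ(g) - φ(f)] × [1/(1 - f + g) + 1/(1 + f - g)]

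With ρ = 0.5:

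| f (intervention stops) | g (control crosses over) | Bias, SD |
|---|---|---|
| 0.10 | 0 | -0.177 |
| 0.20 | 0.10 | -0.106 |
| 0.10 | 0.10 | 0 |
| 0.10 | 0.20 | +0.106 |
| 0 | 0.10 | +0.177 |

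For the second row: 0.5 × (0.1755 - 0.2800) × (1/0.9 + 1/1.1) = -0.0522 × 2.0202 = -0.106. The fourth row is its mirror image. When f = g, the first bracket is zero and the bias vanishes.

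A bias in favour of continued cupping therefore follows only if stopping in the intervention arm outweighs crossover among controls. The protocol gives no information on either.

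**The case for a change.** The strongest argument for a change is that this is more than silence on an analysis population. The protocol does state the compared groups, and it does so by treatment continuation. An SAP that followed the sentence to the letter would analyse as treated. The sentence describing the arms says what each arm does, not where a patient who departs from it is counted. Rewording costs one sentence and would do no harm if shorthand was meant all along.

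Part of this stands. The labels are not explicitly tied to the arms, a literal reader could misapply them, and an as-treated primary comparison would be unsound. The arithmetic for one-directional stopping is also correct.

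The rest does not carry the point. To reach an as-treated rule, the reader must detach the comparison sentence from the sentences that introduce the groups in the same terms. That departures are likely is an inference from the setting; the protocol reports no stopping, crossover or outside cupping. It is also an inference that patients knew whether they were being cupped. That inference is reasonable given the procedure, although the text uses the words double blind of the assignment. Collecting the sessions actually received at each follow-up may no longer be possible, since the text is in the past tense and describes patients presenting from May 2016 to January 2018.

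**Conclusion.** The concern does not call for a change. On the natural reading, Group 1 is the arm randomised to continue WCT and Group 2 the arm randomised to stop, so the stated comparison is the randomised one. Spelling this out would record a definition the context already supplies and would leave the design and the comparison as they are. A statistician working from this text would ordinarily analyse patients as assigned. The treatment of departures belongs in the SAP, which is not shown, and its absence from the protocol is not a fault.

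This conclusion rests on reading the labels in context. It would change if an SAP or report were found to have reclassified patients by treatment received. Even then, the illustrative bias runs from -0.29 to +0.18 SD over the assumed cases examined here, so neither its size nor its sign could be settled from the protocol.

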The migraine disability score is a scale evaluating disability and loss associated with migraine. It consists of 7 questions, the 1st, 3rd and 5th of which evaluate the days lost from school, work, housework or leisure activities because of headaches in the last 3 months. The 2nd and 4th questions evaluate the number of additional days lost from work or housework in the last 3 months due to a reduction in productivity (defined as at least a 50% reduction in productivity). An additional two questions (MIDAS A and B) evaluate the frequency of headaches and the severity of the headaches using a visual analog scale (VAS), but these are not added to the total MIDAS score. The total MIDAS points are obtained from the total of the first 5 questions. Total points of 0-5 = 1st degree (very little or no restriction), 6-10 points =2nd degree (mild or occasional restriction), 11-20 points = 3rd degree (moderate level of restriction), and 21 + points = 4th degree (severe restriction).

Wet cupping technique

CT was applied using plastic disposable vacuum cups on the back in the 5 areas of C7 cervical spine (DU14 acupoint), T2-4 lateral spine bilaterally (BL41-42 acupoint) and T6-8 lateral spine bilaterally (BL44-46), which are the recommended sites for headache (12). The cupping technique procedure was conducted in five phases:

1. Primary suction; the cups are placed on the selected area with a manual suction pump which draws air out from inside the cups. The cups are left attached to the skin for 5 minutes. The skin and subcutaneous tissue swells.

2. Area disinfection; the swollen areas are wiped with sterile gauze after disinfection with povidone iodine.

3. Scarification; Superficial incisions (20-30 gauge), 5 mm length and 1-2 mm depth, are made on the skin with a sterile, number 11 surgical blade.

4. Bloodletting and secondary suction; the cups which had been previously removed are placed again on the scarified areas using a manual pump in the same way as described above. Blood leaks from the capillary vessels of the skin and subcutaneous tissue and fills the cups, which are left in place for 15 minutes.

5. Removing and dressing; the cups full of blood are removed after 15 mins. The areas of application are wiped with sterile gauze and then a dressing is applied.

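### Does the absence of a MIDAS score for months 6 to 9 undermine the randomised comparison?

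*Protocol*

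**What the plan says.** The relevant statements are in two sections of the Protocol.

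- **MIDAS, recall period.** Questions 1, 3 and 5 "evaluate the days lost from school, work, housework or leisure activities because of headaches in the last 3 months". For the remaining scored items, "The 2nd and 4th questions evaluate the number of additional days lost from work or housework in the last 3 months".
- **MIDAS, scoring.** "The total MIDAS points are obtained from the total of the first 5 questions". The two further items, on headache frequency and severity, do not enter the total.
- **Study design and Patient selection, randomisation.** "At the end of the 3rd month patients were allocated into two parallel arms".
- **Study design and Patient selection, assessments.** After the baseline score, "MIDAS was applied again at the end of the 6th and 12th months to both of the groups". No month-9 assessment is described.
- **Study design and Patient selection, comparison.** "Disability values in the 6th and 12th months were evaluated with MIDAS between those who continued treatment (Group 1") and the group that stopped (Group 2).

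No statement in the document says that the scores cover the whole period after randomisation.

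**The concern.** The trial asks what happens when treatment is continued rather than stopped, and it follows patients for nine months after randomisation. One would naturally want to know when benefit fades and how many days are lost in all. MIDAS counts days over a fixed look-back of 3 months, while the last two assessments are 6 months apart, so the second score does not reach back to the first.

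If the trial needed the whole period, three things would be lost: any worsening confined to months 6 to 9, a closer dating of later relapse, and the total number of days lost since randomisation. Days that patients were never asked about cannot be restored by analysis, so this could not be left to a statistical analysis plan.

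**Working it through.** **Inputs.** Recall period 3 months for all five scored questions (MIDAS section). Randomisation at the end of month 3, MIDAS at the ends of months 6 and 12 (Study design and Patient selection). The protocol states no coverage figure to reproduce. I assume that assessments fall exactly at the stated times, since no visit windows are given.

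**Step 1: coverage.** A score at month *v* describes months *v* − 3 to *v*.

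| Item | Calculation | Result |
|---|---|---|
| Randomised period | 12 − 3 | 9 months |
| Month-6 score | 6 − 3 to 6 | months 3 to 6 |
| Month-12 score | 12 − 3 to 12 | months 9 to 12 |
| Covered | 3 + 3 = 6; 6/9 | 67% |
| Not covered | 9 − 6 = 3; 3/9 | 33% (months 6 to 9) |

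The gap is real. The month-6 window also begins exactly at randomisation, so that score contains no days from the run-in, when every patient was treated.

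**Step 2: what the stated comparisons need.** Write D(3–6), D(6–9) and D(9–12) for the difference between arms in MIDAS points in each 3-month window. The protocol's two comparisons estimate D(3–6), from the month-6 score, and D(9–12), from the month-12 score. D(6–9) enters neither. It would be needed only for the sum D(3–6) + D(6–9) + D(9–12), the difference in total days lost, and the protocol does not name that sum as an outcome.

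**Step 3: what the gap can hide.** Take one patient at 10 points per window (top of the 2nd degree) who may step up to 21 (bottom of the 4th degree). The band limits are the protocol's; the step is an assumption.

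| Course | Points in months 3–6, 6–9, 9–12 | Total | Recorded at months 6 and 12 |
|---|---|---|---|
| No worsening | 10 + 10 + 10 | 30 | 10 and 10 |
| Worse in months 6–9 only | 10 + 21 + 10 | 41 | 10 and 10 |
| Worse from end of month 9 | 10 + 10 + 21 | 41 | 10 and 21 |
| Worse from end of month 6 | 10 + 21 + 21 | 52 | 10 and 21 |

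The same pair of scores can thus go with different totals: an excess over 30 of 52 − 30 = 22 points or 41 − 30 = 11 points. The recorded scores are nevertheless correct for their own windows in every row. Only the total and the onset are ambiguous, and the protocol asks for neither. Lasting worsening shows at month 12. To be missed altogether, worsening must begin after month 6 and be fully reversed by month 9. To alter a conclusion about the arms, that pattern would also have to differ systematically between them. The document gives no reason to expect this.

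**The case for a change.** The strongest case on the other side is that the schedule suits the question poorly. In a trial of stopping treatment, the course after stopping is the natural interest. Windows of 3 months at months 6, 9 and 12 would tile the randomised period without gap or overlap, and the cost would be one short questionnaire and one contact per patient. A rise first seen at month 12 can be dated only to an interval of 12 − 6 = 6 months, whereas a month-9 score would narrow this to 3. A reader might also take the 12-month result for the state of patients throughout follow-up.

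The arithmetic in this stands, and so does the point that the missing days cannot be recovered. The rest does not make a defect. Timing of relapse and total days lost are objectives brought to the protocol from outside; the stated objective is comparison at two times. Spaced assessments with a fixed look-back are an ordinary design choice. The value of a total over months 3 to 12 also depends on how long the arms differed in treatment, and the document says only that one group continued, without frequency or end date. A month-9 score would still not show change since randomisation, because no month-3 score is described. Misreading the 12-month result is already guarded against, because the MIDAS section states the look-back for every scored question.

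**Conclusion.** The concern does not hold. Months 6 to 9, 3 of the 9 randomised months, are described by no MIDAS score, but this contradicts nothing in the protocol and makes no stated comparison invalid. The month-6 and month-12 scores are comparisons of randomised groups over months 3 to 6 and months 9 to 12. The gap is the same in both arms, and the effect of the missing window on either stated comparison is nil. What is forgone is information on a total and a time course that the protocol does not set out to measure.

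This rests on assessments falling at the stated times and on the protocol's objective being what it says: disability compared at months 6 and 12. If a report claimed cumulative disability, or the timing of relapse to within 3 months, the data would not support that claim. The protocol makes no such claim. A month-9 questionnaire would be a matter of preference, not the correction of an error.

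### Phase 4 of the wet cupping procedure returns cups from skin not yet disinfected to fresh incisions; a new sterile cup would be a cheap safety improvement

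*Protocol*

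**What the plan says.** The protocol's Wet cupping technique section describes the cups and then lists five phases in order.

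- Opening paragraph: "CT was applied using plastic disposable vacuum cups on the back in the 5 areas". The cups are called disposable; whether they are sterile is not stated.
- Phase 1 (primary suction): "The cups are left attached to the skin for 5 minutes". No disinfection is listed before this.
- Phase 2 (area disinfection): "the swollen areas are wiped with sterile gauze after disinfection with povidone iodine".
- Phase 3 (scarification): "Superficial incisions (20-30 gauge), 5 mm length and 1-2 mm depth, are made on the skin", using a sterile blade.
- Phase 4 (bloodletting and secondary suction): "the cups which had been previously removed are placed again on the scarified areas". Blood then "fills the cups, which are left in place for 15 minutes".
- Phase 5: the cups come off, the areas are wiped with sterile gauze and a dressing goes on.

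On frequency, Study design and Patient selection says that "WCT was applied once a month, 3 times (Day 0, 30, 60") for every patient. After randomisation at the end of month 3, Group 1 continues the treatment for a number of sessions that is not stated, and Group 2 stops.

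**The concern.** The order of the steps matters here. The cup meets the skin before the povidone iodine does, and the same cup goes back after the skin has been opened. Nothing listed between those two contacts cleans or replaces it. An operator who follows phase 4 to the letter therefore puts an item that has been on undisinfected skin over open incisions.

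What is at stake is patient safety: an avoidable chance of carrying the patient's own skin flora back to an area that phase 2 has just disinfected. It recurs at every session, and the protocol gives no reason for using the same cup twice. No statistical property of the trial is involved.

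**Working it through.** The protocol states no figure to reproduce on this point, so the check is a trace of the cup and the skin through the five phases, followed by a count of cups to size the fix.

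**Trace**

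| Phase | Skin | Cup |
|---|---|---|
| 1 | Not disinfected by any listed step | On the skin, 5 minutes |
| 2 | Disinfected with povidone iodine, wiped with sterile gauze | Not mentioned |
| 3 | Cut 1-2 mm deep with a sterile blade | Not mentioned |
| 4 | Open incisions | Same cup back on, 15 minutes |
| 5 | Wiped with sterile gauze, dressed | Removed |

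Three things follow.

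1. The cup's first contact comes before the only listed disinfection.
2. That disinfection is applied to the skin areas. The cup is not part of it.
3. The blade in phase 3 and the gauze in phases 2 and 5 are called sterile. From the moment of incision to the end of bloodletting, the cup is the one listed item on the wound that is not described as sterile or disinfected. (The phase 5 dressing is not called sterile either, but nothing in the text puts it on undisinfected skin first.)

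**Count of replacement cups**

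Inputs: the areas in the opening paragraph and the three sessions in Study design and Patient selection. Assumption: one cup per area, since cups per area are not stated.

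- Areas: C7 (1) + T2-4 on both sides (2) + T6-8 on both sides (2) = 5, which matches the stated 5.
- Extra cups per session: 1 × 5 = 5.
- Over Day 0, 30 and 60: 5 × 3 = 15 per patient.
- Group 1, with k further sessions: 15 + 5k. The protocol does not give k, so no total is possible.

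These counts size the fix. They do not measure infection risk, and the protocol offers nothing from which that risk could be calculated.

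**The case against.** The strongest reply is that the list of phases is plainly incomplete. Removal of the cups after phase 1 has no step of its own and is known only because phase 4 refers back to it. If the text omits the removal, it may equally omit a wipe or a rinse, and the absence of the word sterile does not show that the cups were non-sterile. This stands as far as it goes: one cannot conclude that the clinic used contaminated cups. It does not dispose of the point, because phase 4 is not silent. It names which cups go back, and a fresh cup would depart from the written instruction.

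The word disposable does not settle it either. It suggests that a cup is discarded after use, but it does not supply a clean one between phases 1 and 4 of the same session.

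It can also be said that the harm is small and undemonstrated. Blood flows outward into the cup under suction, the flora are the patient's own, a dressing follows, and patients with infection, bleeding disorder or widespread skin disease are excluded. All of this stands. It limits the point to a modest one.

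A reader might infer that the procedure breaks its own rule of disinfecting skin before cutting it. It does not. Phases 2 and 3 meet that rule at the moment of incision, and the shortfall concerns only what is placed on the wound afterwards.

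**Conclusion.** The point holds as a cheap patient-safety improvement to a written instruction. Followed literally, phase 4 puts a cup with prior contact on undisinfected skin over open incisions at 5 areas for 15 minutes. This happens at three sessions for every patient and at an unstated number of further sessions in Group 1. The added infection risk cannot be sized.

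The conclusion rests on reading phase 4 as it is written and on no cleaning step having been left out of the text. If cups were cleaned or changed in practice, the defect is in the wording alone.

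Three stronger readings are not supported:

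- **Reuse between patients.** The text shows reuse within one patient and one session only.
- **An effect on the results.** Group 1 has more sessions than Group 2, but nothing in the protocol links cup handling to the MIDAS scores, and the comparison at months 6 and 12 is unaffected.
- **A larger number of cups.** One cup for each named acupoint would give 1 + (2 × 2) + (3 × 2) = 11 per session and 11 × 3 = 33 over three sessions. The acupoint ranges label the five stated areas, and nothing suggests a separate cup for each acupoint, so 5 per session is the natural reading.

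**What to change.** Reword the opening of phase 4 to say: *a new, sterile single-use cup is placed on each scarified area*. Apply it at all sessions, before and after randomisation.

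The cost is about 5 extra cups per session on the assumption of one cup per area: 15 per patient over the three common sessions, plus 5 for each further Group 1 session. The protocol gives no cup price, so calling this cheap is a judgement based on the cups already being disposable plastic. It needs no extra staff or visits and leaves the sample size and analysis unchanged.

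The protocol gives its inclusion period as May 2016 to January 2018 and is written partly in the past tense, so the change matters chiefly for any continued or repeated use of the procedure.
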